9.0 TREATMENT/INTERVENTION PLAN

Patients will be prescribed twice daily use of topical ruxolitinib 1.5% cream (randomized half of face/body) and vehicle/moisturizer (for contralateral side of face/body) to a maximum of 20% BSA on each side for 28 ± 3 days. Topical ruxolitinib will be provided as topical cream.

In the morning and evening (at least 60 minutes before bedtime), patients will be instructed to apply a pre-designated number of fingertip units of each topical intervention (ruxolitinib and moisturizer) to each side of the face/body unit as outlined in provided photograph for each side. Patients will receive detailed instructions at the baseline visit and receive clear, written instructions on the standardized application technique (see Patient Instructions: Topical Medications). Patients will apply topical ruxolitinib cream and vehicle cream to the equivalent BSA on each side (e.g., if one side has

MEMORIAL SLOAN KETTERING CANCER CENTER IRB PROTOCOL

15% lesional skin and contralateral side has 10% lesional skin, the subject will treat only 10% on each side) and no more than to 20% BSA on each side.

Before topical applications, patients will be instructed to gently wash the face and body with a gentle cleanser (examples include Cetaphil, Purpose, Aveeno, Vanicream products) and pat skin dry with a clean towel. Patients will not be encouraged to apply topical emollients to the treated face and body during the study, but if desired, they may apply to untreated areas. Patients will be advised not to use products with chemicals or perfumes.

We do not anticipate the need for any adjustments to the treatment plan as consequence of adverse reactions to ruxolitinib (see section 11.0), but any patients with adverse cutaneous reactions to treatment with topical ruxolitinib 1.5% cream, or moisturizer will be advised to return to clinic to see a dermatologist right away. Adverse event reporting will be based on CTCAE v5.0, as applicable[22].

In the event of a patient emergency, the principal investigator and study pharmacist will be able to unblind the patient.

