10.2 Study Assessments

The subjects will be assessed by the study dermatologist on day 0,1, 14, at the end of study day 28 days, at the safety visit 4 weeks later (day 56), as well as 28 days after last dose of study drug for subjects who continue in the open-label extension (day 84). The assessments will include (Table 1):

Clinical assessment:

- Skin examination with calculation of:
 - **Lesional Body Surface Area:** As per the 2014 NIH consensus criteria for chronic GVHD: Body surface area calculation of each face/body side that will be targeted with topical therapy will be performed by the study dermatologist on study visit on day 1, 14 \pm 3 days, 28 \pm 3 days, 56 \pm 5 days[, and day 84 \pm 5 days for subjects who continue in the open-label extension]. Patient will be photographed, and subsequently treatment-targeted BSA will be additionally calculated from these study visit photos by

MEMORIAL SLOAN KETTERING CANCER CENTER IRB PROTOCOL

one bone marrow transplantation hematologist blinded to treatment side. Standardized photography will be performed at each evaluation visit. (Table 1, Appendix I-II). Marked treatment areas will not change if improvement or worsening is seen.

- **Physician's Global Assessment of Clinical Condition (PGA):** area calculation of each face/body side will be performed by the study dermatologist on study visit on day 1, 14 ± 3 days, 28 ± 3 days, 56 ± 5 days [, and day 84 ± 5 days for subjects who continue in the open-label extension] (Appendix IV)
- **Composite Assessment of Index Lesion Severity (CAILS) for each side:** area calculation of each face/body side will be performed by the study dermatologist on study visit on day 1, 14 ± 3 days, 28 ± 3 days, 56 ± 5 days[, and day 84 ± 5 days for subjects who continue in the open-label extension] (Appendix V)
- **Adverse events** will be assessed and graded as per the Common Terminology Criteria for Adverse Events (CTCAE) version 5.0, and as applicable.
- **Patient-reported outcomes assessment:** Patients will complete an adapted skin-specific PRO-CTCAE™ on study visit on day 1, 14 ± 3 days, 28 ± 3 days, 56 ± 5 days[, and day 84 ± 5 days for subjects who continue in the open-label extension] for each side of the face/body (two questionnaires in total per visit). (Table 1, Appendix III). This questionnaire should take patients less than 10 minutes to complete.

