14.0 BIOSTATISTICS

Target sample size is 24 patients, wherein 12 patients will be randomized to topical ruxolitinib to right side and 12 patients to the left side, with placebo cream on contralateral side. For each side of the face/body, non-sclerotic and superficially sclerotic chronic cutaneous GVHD BSA, PGA, and CAILS will be assessed in real-time by the study dermatologist observer blinded to the treatment status. The methodology for the real-time BSA calculation is available in Appendix I,II. The efficacy endpoint for the primary objective will be the difference in body surface area (BSA) as recorded by the dermatologist of non-sclerotic and superficially sclerotic cutaneous cGVHD between the topical ruxolitinib and vehicle treated sides of the face/body at study day 28. In this pilot study, we are utilizing three different measures to assess efficacy to qualitatively evaluate which works best for the clinician within the context of the patient visit. The bone marrow transplantation oncologist will subsequently calculate the BSA via total body photographs taken during the visit. Maximum BSA for topical ruxolitinib application will be 20% of overall BSA. All BSA, PGA, and CAILS assessments performed at study days 14 ± 3 days and study day 28 ± 3 days will be performed by the study dermatologist in real-time and serve as the data for the efficacy analysis. All BSA will also be calculated virtually by one bone marrow transplantation hematologist in review of total body photographs performed during visit, blinded to treatment, but will not contribute to efficacy assessments. Participants will only be included in the primary endpoint analysis if they complete the 28 ± 3 days assessment. Descriptive statistics and graphical methods will be employed to evaluate participant characteristics and the distribution BSA, PGA, and CAILS differences at each evaluation time point. Paired t-tests will be performed to assess differences in BSA. In addition, since the overall area treated may vary slightly between participants, we will use linear regression with the difference between treatment and control areas at day 28 as the dependent variable, and the total

**MEMORIAL SLOAN KETTERING CANCER CENTER
IRB PROTOCOL**

treatment area BSA as the independent variable. Regression coefficients along with 95% confidence intervals will be reported for this treatment area adjusted difference.

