The primary aim is to assess the efficacy of ruxolitinib 1.5% cream for the treatment of non-sclerotic and superficially sclerotic chronic cutaneous GVHD at day 28 visit. This is a pilot study. With the average body surface area for male and female adult cancer patients has been estimated to be 1.9m² and 1.7m², respectively[26]. Using an average BSA of 1.8m² (18,000 cm²) for our mixed sample; if we treat, on average, 5.0% BSA per participant, we expect to have equivalent areas of 0.09m² or 900cm² of treatment and control areas per participant.

Table. Effect size calculations for the minimum detectable difference in area between treatment and control sides of the participant based on varying levels of correlation between treatment and control areas within participant.

Effect Size	Difference in area between treatment and control areas (cm ²)	Control area (cm ²)	Treatment area (cm ²)	SD of the difference	SD Control area	Correlation between treatment and control areas
-0.5972	-400.6	900	499.4	670.8	500	0.1
-0.5972	-377.7	900	522.3	632.5	500	0.2
-0.5972	-353.3	900	546.7	591.6	500	0.3
-0.5972	-327.1	900	572.9	547.7	500	0.4
-0.5972	-298.6	900	601.4	500	500	0.5
-0.5972	-267.1	900	632.9	447.2	500	0.6
-0.5972	-231.3	900	668.7	387.3	500	0.7
-0.5972	-188.8	900	711.2	316.2	500	0.8

So, based on these estimates, if we select lesional areas on a patient equivalent to 5% BSA (which is roughly 900cm² for both treatment and control sides), and we have an estimated common standard deviation of 500, with 80% power, a two-sided test, an alpha level of 5%, and a correlation between treatment and control areas of 0.4, we can expect to detect a 327.1cm² difference between treatment and control areas at the day 28 evaluation. The effect size calculation is based on a paired t-test. Since we do not have any pilot data for these calculations, the estimate for the standard deviation that utilized for these estimates comes from experience with conditions with a similar presentation. The Table above lists the expected differences between treatment and control areas based on a range of correlations.

Secondary endpoints include:

1. Physician's Global Assessment of Clinical Condition (PGA) at day 28

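### The area-adjusted regression rests on treated area varying only slightly; the plan's own limits and planning figures point to wide variation, and the ordinary 95% interval for the area slope could then cover about 78-93%

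*Combined protocol and SAP*

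**What the plan says.** Section 14.0 names paired t-tests for the difference in BSA between sides. It then adds a second analysis: "since the overall area treated may vary slightly between participants, we will use linear regression with the difference between treatment and control areas". The outcome in that model is the side difference at the day-28 visit, and the only covariate is each patient's total treated area. On reporting it says: "Regression coefficients along with 95% confidence intervals will be reported for this treatment area adjusted difference". Section 14.0 promises 95% intervals for no other analysis. The same regression is repeated at day 14 (secondary endpoint 3). Nothing is said about unequal variance, robust errors, weighting, transformation, residual checks or centring of the area.

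Four other statements bear on how much treated area can vary:

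- Section 6.1 requires at least 2% BSA of disease in total and sets no floor per side.
- Section 9.0 matches the area on the two sides and caps it: "no more than to 20% BSA on each side". Its worked example treats 10% per side.
- Section 14.0 plans on 5% per side ("if we treat, on average, 5.0% BSA per participant", 900 cm²) and states "we have an estimated common standard deviation of 500".
- Section 10.2 fixes the area: "Marked treatment areas will not change if improvement or worsening is seen".

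**The concern.** The limits and planning figures describe treated areas that may differ many-fold between patients, not slightly. That matters because the dependent variable is an absolute area difference inside a fixed marked region. A patient with 1% marked per side cannot show a difference beyond ±1% BSA; a patient with 20% marked can show up to ±20%. Ordinary least squares (OLS) takes the residual spread to be the same for both.

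If the spread grows with area, the patients with large areas have both the most leverage on the slope and the noisiest differences, so the usual standard error of the slope is too small. The practical risk is a pilot report that benefit depends on treated area when the evidence for this is weaker than the interval suggests. The stated objective is preliminary efficacy estimates, so a reported interval should mean what it says.

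**Working it through.** **1. The plan's own figure.** "Target sample size is 24 patients", each giving one paired difference. With common SD 500 and correlation 0.4, the SD of the difference is 500 × √(2 × (1 − 0.4)) = 547.7 cm². The noncentral t distribution gives 80.0% power for a two-sided 5% paired t-test at a standardised effect of 0.5972 with n = 24, and 0.5972 × 547.7 = 327.1 cm². The plan's figure is reproduced. It concerns the paired t-test, not the regression.

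**2. How much area can vary.** On 18,000 cm², 1% is 180 cm² and 20% is 3,600 cm². The permitted range per side is therefore 3,600 / 180 = 20-fold with an even split of the 2% floor, or 10-fold if the floor is read as 2% per side. The planning figures give a coefficient of variation of 500 / 900 = 56%, and 500 cm² is 2.78% BSA. The SD of 500 is stated for the areas in the power calculation; using it for the baseline treated area is an assumption. At 900/500, the largest of 24 treated areas is typically 7 to 8 times the smallest.

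**3. Why spread should follow area.** Let A be the marked area per side and f the fraction still involved at day 28. The difference is D = A × (f_ruxolitinib − f_vehicle), so |D| ≤ A. This takes BSA to be counted within the marked area, as section 10.2 and the CAILS size table indicate. The bound makes growing spread likely. It does not say how fast the spread grows.

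**4. Coverage of nominal 95% intervals.** Simulation with n = 24 and D regressed on area. Area was drawn with mean 900 and SD 500 cm², then limited to 180-3,600 cm². After that limit the mean/SD is about 897/480 (lognormal), 913/490 (gamma) and 976/435 (normal). SD(D) was constant, proportional to √A, or proportional to A. Using total area 2A instead of A changes nothing here.

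| Area distribution | SD(D) | Slope, OLS | Slope, HC3 | Slope, weights 1/A² | Difference at sample mean area, OLS |
|---|---|---|---|---|---|
| Lognormal | constant | 95% | 95% | 90% | 95% |
| Lognormal | ∝ √A | 88% | 92% | 95% | 94% |
| Lognormal | ∝ A | 78% | 91% | 95% | 93% |
| Gamma | constant | 95% | 95% | 88% | 95% |
| Gamma | ∝ √A | 90% | 93% | 94% | 95% |
| Gamma | ∝ A | 81% | 91% | 95% | 94% |
| Normal | constant | 95% | 95% | 84% | 95% |
| Normal | ∝ √A | 93% | 94% | 92% | 95% |
| Normal | ∝ A | 89% | 93% | 95% | 94% |

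For SD ∝ A:

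- The OLS interval for the difference at a fixed 900 cm² covers 92% (lognormal), 93% (gamma) and 96% (normal).
- The uncentred intercept covers 90%, 93% and 97%, so it can err either way.
- The paired t-test keeps 94-95%.
- With 20 completers, OLS slope coverage is 79%, 82% and 90%, almost the same as with 24.

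**5. Bounded model.** With beta-distributed fractions remaining and correlation 0.4, OLS slope coverage is again about 78% (lognormal), 81-82% (gamma) and 89-90% (normal). With no drug effect, the slope is then declared significant in 22%, 20% and 10% of trials, against a nominal 5%.

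**6. Relative outcome.** In the same bounded model, with 50% against 70% of the marked area remaining, a paired t-test on the fraction has 94% power and one on raw BSA 87-90%. That gain depends on the spread being roughly proportional to area.

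**The case against.** The strongest reply is that the harm is narrow. The regression is an additional analysis in a 24-patient pilot. The slope on area is not the treatment effect. The paired t-test, named first and used for the power calculation, holds its level, and the adjusted difference near the mean area loses little. All of this stands.

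It is also fair that the documents give no relation between variance and area, and no SD for the baseline treated area. A reader might infer that real slope coverage is 75-78% at the plan's own mean and SD. The documents do not support that. About 78% needs a strongly right-skewed area distribution and spread fully proportional to area; 75% appeared only with a log-uniform area whose mean and SD (1,142 and 925 cm²) are not the plan's. A reader might also infer that a 20-fold range is expected among the enrolled patients. It is what the rules permit, and at 900/500 about 7- to 8-fold is typical.

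Relative measures are not absent either: PGA grades percentage change, and CAILS is analysed as a ratio to baseline. Neither is a relative form of the primary BSA outcome, so a small addition is still useful.

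The reply does not rescue the premise. Slight variation remains at odds with sections 6.1, 9.0 and 14.0, and the plan reports the regression coefficients with intervals but makes no provision for unequal spread.

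**Conclusion.** The concern holds in a limited form. The stated reason for the regression conflicts with the plan's own limits and planning figures, and constant variance is unlikely because each difference is bounded by a fixed marked area. If the spread grows with area, the nominal 95% OLS interval for the area slope covers about 78-93% with n = 24; it covers 95% if the variance is constant. Where in that range it falls depends on the area distribution, the rate at which the spread grows, and the borrowed SD of 500 cm².

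It would go too far to say that all the reported intervals are too narrow or that the primary analysis is compromised. The difference at or near the mean area keeps about 92-96%, the paired t-test 94-95%, and the uncentred intercept can even be too wide. This is a cheap improvement to a supplementary analysis, not a flaw in the primary comparison.

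**What to change.** In section 14.0, for the regression at day 28 and at day 14:

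1. Delete 'slightly'.
2. Centre total treated area at its sample mean, so that the intercept is the adjusted difference at mean area and is itself a reported coefficient.
3. Report HC3 heteroscedasticity-robust standard errors with t critical values. Slope coverage rises to about 90-95%. This does not fully restore 95% when the spread is proportional to a skewed area, but it costs almost nothing if the variance is constant.
4. Add, as a supportive sensitivity analysis, a paired t-test on each side's BSA at the visit as a percentage of its marked BSA. State that it answers a relative question and is more powerful than raw BSA only if the spread is roughly proportional to area.

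Keep the paired t-test on BSA as it is. Do not make weights of 1/area² the default: they restore about 95% if the SD is proportional to area, but slope coverage falls to about 84-90% if the variance is constant.

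The cost is a few sentences and one line of code, with no new data. Slope intervals will usually be wider, and one extra relative estimate is reported.

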2.0 OBJECTIVES AND SCIENTIFIC AIMS

Primary Objective:

- To obtain preliminary efficacy estimates of ruxolitinib 1.5% cream for the treatment of non-sclerotic and superficially sclerotic chronic cutaneous GVHD at day 28 as determined by the body surface area (BSA) of the GVHD rash on the side of the face/body treated with topical ruxolitinib cream versus contralateral side treated with vehicle at day 28 visit when applied beginning on day 1.

Secondary Objectives:

- To obtain preliminary efficacy estimates of ruxolitinib 1.5% cream for the treatment of non-sclerotic and superficially sclerotic chronic cutaneous GVHD at day 28 as determined by the Physician's Global Assessment of Clinical Condition (PGA) of the

MEMORIAL SLOAN KETTERING CANCER CENTER IRB PROTOCOL

GVHD rash on the side of the face/body treated with topical ruxolitinib cream versus contralateral side treated with vehicle at day 28 visit when applied beginning on day 1.

- To obtain preliminary efficacy estimates of ruxolitinib 1.5% cream for the treatment of non-sclerotic and superficially sclerotic chronic cutaneous GVHD at day 28 as determined by the objective Composite Assessment of Index Lesion Severity (CAILS) of the GVHD rash on the side of the face/body treated with topical ruxolitinib cream versus contralateral side treated with vehicle at day 28 visit when applied beginning on day 1.
- To obtain preliminary efficacy estimates of ruxolitinib 1.5% cream for the treatment of non-sclerotic and superficially sclerotic chronic cutaneous GVHD at day 14 as determined by the body surface area (BSA), Physician's Global Assessment of Clinical Condition (PGA), and the objective Composite Assessment of Index Lesion Severity (CAILS).
- Compare the difference in patient-reported outcomes between the side of the face and body treated with topical ruxolitinib cream versus the contralateral side treated with twice daily vehicle at day 14 visit and day 28 visit using the adapted National Cancer Institute Patient-Reported Outcomes version of the Common Terminology Criteria for Adverse Events (PRO-CTCAE™) questionnaire
- Compare the difference in chronic cutaneous non-sclerotic and superficially sclerotic GVHD BSA between the sides of the face/body treated with topical ruxolitinib and vehicle by measuring the agreement of blinded independent physician's review of standardized photography of the right and left sides of the face and body respectively performed at day 28 visit

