8.0 PRETREATMENT EVALUATION

Patients may be screened and consented starting from up to 7 days before study initiation.

The following initial baseline procedures can take place at any time during this period, or on the day of initiation (Day 1)

1. Medical history, including concomitant medications
2. Study assessments (serve as baseline measures for the study):
 - Patient-reported Outcomes (Appendix III):
 - Adapted PRO-CTCAE™ for each side of face/body affected by GVHD rash
 - Clinical assessments (Appendices I, II, IV, V)
 - Skin examination with calculation of body surface area (BSA), Physician's Global Assessment of Clinical Condition (PGA), and the objective Composite Assessment of Index Lesion Severity (CAILS) for each side
 - Standardized photography and 3D photography
 - During the first and third study visit, if the participant gives consent, the research photographer will take 3D photography, also called Total Body Photography of the patient.

MEMORIAL SLOAN KETTERING CANCER CENTER IRB PROTOCOL

- For each side, the skin area targeted for treatment will be outlined with surgical marker, photographed, and a photograph of each outlined target treatment area will be provided to the patient as an application reference.
- Laboratory investigations
 - Laboratory analyses and skin biopsy will be performed only as clinically indicated for routine care.
 - Minimally invasive skin tape strip RNA sequencing will be performed on each face/body side by the study dermatologist (Appendix VIII)

Visit # Study day:	Pre-study Screening or Day 1
Reason for visit	
Informed consent	X
Medical history	X
Pregnancy test (if applicable for females of child-bearing potential)	X
Clinical assessment (i.e., BSA, PGA, and CAILS on each side; adverse events/CTCAE assessment)	X
Skin examination	X
Lesional skin tape stripping on each side	
Patient-reported outcomes questionnaire for each side	X
Standardized photography	X
Drug application	X
Drug diary return	X
Drug accountability	X

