The difference in the PGA score of non-sclerotic and superficially sclerotic cutaneous cGVHD between the topical ruxolitinib and vehicle treated sides of the face/body will be calculated. The Wilcoxon signed rank test will be used to assess differences in these paired assessments for the day 28 assessment.

MEMORIAL SLOAN KETTERING CANCER CENTER IRB PROTOCOL

2. Composite Assessment of Index Lesion Severity (CAILS)

The difference between the ratios of the day 28 CAILS score to baseline CAILS score of non-sclerotic and superficially sclerotic cutaneous cGVHD between ruxolitinib treated side and vehicle treated sides of the face/body at study completion. We will use descriptive statistics to describe the distribution of the difference in CAILS ratios between treated and vehicle sides of the body. The difference in ratios will be assessed using a paired t-test.

3. Efficacy at day 14

Little is known about the efficacy of this treatment in this patient population. As a secondary aim, we will assess efficacy at the 14 day visit as we described for the primary aim of the study using paired t-tests and linear regression to control for potential differences in overall treatment areas between study participants.

4. Patient-reported Outcomes

Patient reported outcomes measured by the NCI Patient Reported Outcomes-Common Terminology Criteria for Adverse Events (PRO-CTCAE™) for each side of face/body affected by GVHD rash; a Likert-scale patient-reported assessment of change in the treated areas has been appended to adapt the PRO-CTCAE™ for this study. PRO-CTCAE™ instrument will be scored as ascribed by methods published for this instrument. Overall summary measures and subdomain measures will be summarized using descriptive statistics. To evaluate differences in the paired responses, for the overall PRO-CTCAE score and for each of the subdomain scores, the Wilcoxon signed rank test will be used.

5. Agreement between GVHD BSA Measurements

GVHD BSA measurements will be evaluated during the patient visit by a dermatologist, and by an additional bone marrow transplant physician using digital clinical images captured during the patient visit. The GVHD BSA assessments for both evaluations will be visually assessed using scatterplots of the two independent assessments and compared using Lin's concordance correlation coefficient.

6. Safety and Tolerability

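### The signed-rank test planned for PRO-CTCAE names no baseline term although each side has a baseline questionnaire; the test is valid, but a baseline-adjusted estimate alongside it could gain precision

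*Combined protocol and SAP*

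**What the plan says.** The secondary objective in section 2.0 compares the ruxolitinib side "versus the contralateral side treated with twice daily vehicle at day 14 visit and day 28 visit", and section 12.0 repeats this as outcome (4). Section 14.0, item 4, gives the analysis: descriptive summaries, then a test introduced by "To evaluate differences in the paired responses", namely that "for the overall PRO-CTCAE score and for each of the subdomain scores, the Wilcoxon signed rank test will be used". On scoring it says only that "PRO-CTCAE™ instrument will be scored as ascribed by methods published for this instrument". No change score, ratio to baseline or baseline covariate is named.

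The baseline data exist. Section 8.0 lists, under "Study assessments (serve as baseline measures for the study", the item "Adapted PRO-CTCAE™ for each side of face/body affected by GVHD rash". Section 10.2 states "Patients will complete an adapted skin-specific PRO-CTCAE™ on study visit on day 1, 14 ± 3 days" and at the later visits, "for each side of the face/body (two questionnaires in total per visit"; the schedule in section 10.0 agrees.

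The two physician-rated severity measures do refer to baseline. CAILS is analysed as a day-28 to baseline ratio on each side (sections 12.0 and 14.0, item 2), and PGA is graded against the baseline condition (section 12.0).

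**The concern.** The plan equalises treated area between the sides, not symptoms. Section 9.0 itself gives an example with 15% lesional skin on one side and 10% on the other, of which 10% is treated on each. One side may therefore itch or hurt more before any cream is applied. If that asymmetry persists, it adds variance to the day-14 and day-28 side differences that a recorded baseline could remove.

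The trial aims at preliminary efficacy estimates from 24 pairs, so precision matters. The signed-rank test as described also yields a p-value and no effect estimate with an interval.

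**Working it through.** **Inputs from the documents.** n = 24 pairs; two-sided 5% and 80% power, stated for BSA only (section 14.0). No SD, effect size or correlation is given for the PRO scores, so these are assumed below.

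**The plan's own figure.** None exists for the PRO comparison. The BSA figure serves as a benchmark. Paired t-test power from the noncentral t distribution with 23 df at effect size 0.5972 is 80.0%, as stated. At correlation 0.4 the SD of the difference is 500 × √(2 × 0.6) = 547.7, and 0.5972 × 547.7 = 327.1 cm². The table is reproduced apart from rounding in its last row.

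**Precision of three analyses.** Let D0 and D1 be the ruxolitinib-minus-vehicle differences at baseline and follow-up, with equal SD and correlation ρ. Relative to the SD of D1, the SD governing the treatment estimate is:
- follow-up difference alone: 1
- difference in change scores: √(2(1 − ρ))
- regression of D1 on D0: √(1 − ρ²)

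Adjustment therefore removes a share ρ² of the variance. Change scores are worse than no adjustment when ρ is below 0.5.

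Power by simulation (normal data, n = 24, 4,000 runs, assumed effect 0.5972 SD of the difference):

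| ρ | Variance removed (ρ²) | Signed-rank, follow-up only | Signed-rank, change | Regression on D0 |
|---|---|---|---|---|
| 0.2 | 4% | 77% | 58% | 79% |
| 0.5 | 25% | 78% | 78% | 89% |
| 0.7 | 49% | 79% | 94% | 96% |
| 0.8 | 64% | 78% | 99% | 99.7% |

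Type I error was 4.6% to 5.3% for all three analyses.

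**Ordinal scores.** Normal data flatter the gain. The next simulations cut an underlying continuous score into five levels (n = 24, all inputs assumed). Here the correlation is the one set before cutting. Entries are adjusted v unadjusted power.

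| Correlation before cutting | Scores well spread | Most scores zero |
|---|---|---|
| 0.3 | 61 v 59% | no gain, or 2–3 points lost, at 0.3 or below |
| 0.5 | 67 v 58% | 35 v 34% |
| 0.7 | 78 v 58% | 41 v 32% |
| 0.8 | 86 v 59% | 48 v 32% |

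Type I error stayed near 5% for both analyses. Other assumed inputs move the levels but give a similar pattern. With an effect of 0.6 per-side SD, well-spread scores and no shared patient effect, unadjusted power was 45–48%, against 47%, 54%, 68% and 80% adjusted. There, change scores gave 32% against 45% unadjusted at a correlation of 0.3.

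Cutting into levels also weakens the correlation. In one five-level run, 0.3, 0.5, 0.7 and 0.8 before cutting became about 0.26, 0.42, 0.61 and 0.70 between the observed differences. The variance removed is then 0.26² = 7%, 0.42² = 18%, 0.61² = 37% and 0.70² = 49%, less than the first table shows for the same nominal values.

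**The case against.** The strongest reply is that nothing here is wrong. A signed-rank test on paired ordinal scores, with the side randomised within patient, is a standard and valid analysis. The endpoint is secondary, the trial is a pilot, and no power claim rests on it. All of that stands, and it limits the point to an efficiency improvement.

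Three stronger readings are tempting, and the documents do not support them.

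- *Baseline asymmetry biases the comparison or could mimic a benefit.* Randomising the side makes the asymmetry chance, which the 5% error rate already covers; simulated type I error is near 5% with or without adjustment.
- *The plan never uses the baseline questionnaire.* Section 14.0 plans descriptive statistics for patient-reported outcomes and does not exclude day 1. What can be shown is that the test names no baseline term. That it uses unadjusted follow-up scores is inferred from how the objective, outcome and analysis are worded, and scoring is deferred to a source outside the documents.
- *The questionnaire plainly covers the whole side, so asymmetry must be large.* The content of Appendices IIIA and IIIB is not in the text available, and no figure for baseline asymmetry is given.

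The plan also appends a Likert item on perceived change in the treated areas. It offers a view of change, but it is the patient's recall and does not adjust the PRO-CTCAE scores.

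Finally, linear regression on differences of five-level scores is not the only choice. That objection is fair, and a rank-based adjusted analysis would also serve, particularly for sparse items.

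**Conclusion.** The point holds as a low-cost gain in precision, not as an error. The planned test keeps its type I error; it leaves unused a covariate that the trial already collects.

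The size cannot be fixed from the documents. On the five-level simulations, the gain is negligible at a correlation of about 0.3 or below, with a loss of a few points when most scores are zero. It is material from about 0.5 upward when scores are well spread, and smaller when most are zero. Every power figure rests on an assumed effect, score distribution and correlation, and is illustrative only. The ordering of the methods is firmer: change scores can lose power against the planned test, while adjustment costs one degree of freedom and at worst a few points of power in the settings examined.

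**What to change.** Add to section 14.0, item 4: for each PRO-CTCAE score at day 14 and day 28, regress the ruxolitinib-minus-vehicle difference on the baseline ruxolitinib-minus-vehicle difference, D1 = α + β·D0 + error, and report α with its 95% CI. Keep D0 centred at zero, meaning no baseline difference, so that α is the expected side difference for a patient with equal sides at baseline. Subtracting the sample mean of D0 would only return the unadjusted mean difference. Where scores are sparse, use a rank-based equivalent.

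Keep the planned signed-rank test alongside it. Do not use simple change scores. Leave the appended Likert change item, which has no baseline value, on the signed-rank test. State the number of pairs in each analysis, since a missing baseline questionnaire removes a pair from the regression only.

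The cost is one sentence and one degree of freedom; no visit or questionnaire is added. It is best written in before the biostatistician is first unblinded, at the interim analysis that section 16.0 sets at 10 evaluable participants.
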